5.3 Study Restrictions

Each subject will be questioned on the specific points listed below prior to drug administration. If a subject admits a non-compliance with these restrictions, the Principal Investigator (or designee) and/or the sponsor will decide whether or not the subject will be permitted to remain in the study. Non-compliance with these restrictions will be recorded.

- Subjects will be instructed to abstain from planning a trip to sunny climate or use of tanning equipment between screening and follow-up visits.
- Subjects will be instructed to abstain from using any drugs/treatments that may influence atopic dermatitis (refer to exclusion criteria and prohibited therapies or procedures section) throughout the study.
- Subjects will be required to start fasting at least 8 hours before drug administration upon waking. Fasting will continue for at least 60 minutes following drug administration, after which subject can have breakfast. Water will be allowed at all times during the fasting period, but no other fluids will be permitted. Medication(s) for other conditions that are permitted in the study can be taken as usual.
- For Baseline (Day 0), week 4 and week 8 visits, a blood draw will be performed for PK analysis. PK samples must be taken pre-dose; therefore, study drug administration will occur during the visit for Day 0 and week 4 visits. Because dosing will occur at the clinic on Day 0 and week 4, subjects will be required to fast for at least 8 hours prior to study drug administration and will be allowed to have a meal 60 minutes after study drug administration.

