7.4 Week 4, Visit 4 (Day 28 ± 2 days)

Subjects are required to fast for at least 8 hours prior to study drug administration. They will be allowed to have a meal 60 minutes after study drug administration.

The following procedures will be performed at this visit:

- Vital signs
- Urine pregnancy test (women of childbearing potential only)
- Physical examination
- Safety labs and biomarkers of inflammation (chemistry, coagulation, hematology, urinalysis, and interleukin profile).
- Pre-dose blood draw pharmacokinetics (if study medication was taken prior to the visit, subject must come back the next day)
- Blood draw total fatty acid profile
- BSA evaluation
- IGA
- EASI assessment
- SCORAD assessment (including VAS pruritus assessment)
- POEM questionnaire
- DLQI questionnaire
- TEWL assessment (for selected sites only)
- Study drug administration (instruct subject that last dose should occur on the day preceding week 8 visit)
- Collection and dispensing of study drug

- Review, collection and dispensing of Subject Compliance log
- Capsule count
- Concomitant medications
- Adverse events evaluation

7.5 Week 8, Visit 5 (Day 56 ± 2 days) (End of Treatment/Early Termination Visit)

The following procedures will be performed at this visit:

- Ongoing medical history review
- Vital signs
- Physical examination
- BMI
- Safety labs and biomarkers of inflammation (chemistry, coagulation, hematology, urinalysis and interleukin profile).
- Serum pregnancy test (women of childbearing potential only)
- Blood draw pharmacokinetics (if study medication was taken prior to the visit, subject must come back the next day)
- Blood draw total fatty acid profile
- BSA evaluation
- IGA
- EASI assessment
- SCORAD assessment (including VAS pruritus assessment)
- POEM questionnaire
- DLQI questionnaire
- TEWL assessment (for selected sites only)
- Collection of study drug
- Review and collection of Subject Compliance log
- Capsule count
- Concomitant medications
- Adverse events evaluation

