Serum Chemistry	Albumin, Alkaline Phosphatase, ALT, AST, Chloride, Cholesterol (non-fasting), CK, Creatinine (Enzymatic), GGT, Glucose Random, LDH, Potassium, Sodium, Total Bilirubin, Triglycerides, Urea (BUN), Uric Acid β-hCG for females of childbearing potential (Screening and week 8 / Early termination)
Urinalysis	Blood, Glucose, pH, Protein
Laboratory Tests Required at Screening only	FSH levels for women greater than 40 and less than 60 years of age who have had a cessation of menses for at least 12 months but less than 24 months.

8.2.4 Total and Free DGLA plasma levels, Total Fatty Acid Profile and Interleukins levels

At Baseline, week 4 and week 8 visits, blood draws will be performed prior to study drug administration (no study drug administration at week 8 visit). If a subject comes to the clinic after taking their daily dose of study medication, this subject will be required to come back the following day for PK blood draws. Total DGLA and free DGLA trough plasma levels will be measured. A second blood draw will be performed for later evaluation of total fatty acid profile in plasma. The blood draw for serum chemistry analysis will be split in two aliquots for chemistry analysis and later evaluation of interleukins.

The date and time of the subject's last dose at home before the visit will be recorded accurately. The study site will instruct subjects not to take their daily study drug dose at home for week 4 visit. Dosing will occur in the clinic during the study visit. The exact time of the sample collection must be recorded.

Blood samples will be processed as soon as possible, no later than 1 hour after blood collection. The plasma obtained will be transferred in polypropylene tubes. Each tube will be labeled in order to identify the analyte to be assayed. All samples will be frozen in an upright position. The detailed instruction for PK, Total Fatty Acid and interleukin sample collection, processing, storage and shipment will be provided in the central laboratory manual. The labels on each tube will include at least the following information:

- Study protocol
- Site number
- Subject identification number
- Visit name
- Analyte name
- Primary (A) or Duplicate (B)

Shipment of the experimental samples will be shipped to ICON Central Laboratories.

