30. The patient-oriented eczema measure: development and initial validation of a new tool for measuring atopic eczema severity from the patients' perspective - correction. *Arch Dermatol.* 2005 Dec;141(3):381.

18 APPENDIX A Study Flow Chart

Visit	Screening	Baseline	Week 2	Week 4	Week 8 / ET visit	Follow up visit / Week 10
Day	-30 to -1	0	14 (± 2)	28 (± 2)	56 (± 2)	70 (±3)
Informed Consent	X					
Demographics	X					
Medical / Surgical History	X	X				
Ongoing medical history ^Y					X	X
Review Inclusion/Exclusion Criteria	X	X				
Hanifin and Rajka criteria	X					
Assign subject identifier number	X					
Randomization		X				
Concomitant Medications	X	X	X	X	X	X ^δ
Safety labs and inflammation biomarkers: Serum Chemistry (including FSH levels at screening when applicable ^Y and interleukin profile), Coagulation, Hematology, urinalysis	X ^Φ	X		X	X	(X ^{**}) ^{Φ, δ}
Pharmacokinetics (pre-dose blood draw) ^{††}		X		X	X	
Blood draw for fatty acid profile sample ^{††}		X		X	X	
Pregnancy Test (β-hCG if female of childbearing potential)*	X	X	X	X	X	X ^δ
Vital Signs	X	X	X	X	X	X ^δ
Physical Examination	X			X	X	X ^δ
BMI	X	X			X	
Study Drug Administration (on site) [€]		X		X	§	
Dispense Study Drug		X	X	X		
Collect Study Drug			X	X	X	
Dispense Subject Compliance Log		X	X	X		
Collect and Review Subject Compliance Log			X	X	X	
Capsule count			X	X	X	
BSA	X	X	X	X	X	X
IGA	X	X	X	X	X	X
EASI assessment		X	X	X	X	X
SCORAD assessment / VAS pruritus assessment		X	X	X	X	X
POEM questionnaire		X	X	X	X	X
DLQI questionnaire		X	X	X	X	X
TEWL (selected sites only)		X	X	X	X	X
Adverse Events [†]		X [†]	X	X	X	X ^δ

*: For women greater than 40 and less than 60 years of age who have had a cessation of menses for at least 12 months but less than 24 months

- **: Only if clinically significant change from baseline in safety lab results at week 8
- *: Serum pregnancy test at screening and week 8 / ET visits, urine test pregnancy for all other visits
- ††: If a subject took study medication prior to the visit, he/she will be required to come back the following day for PK blood draws.
- €: Subjects must be fasting for at least 8 hours before and 60 minutes after drug administration
- §: Subjects will be instructed to take their last study drug dose the day preceding week 8 visit.
- †: Collection of AE will start after the first study drug administration

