Relationship between DGLA levels and the severity of disease will be looked at. A scatter plot of Total and Free DGLA concentrations at baseline versus IGA score at Week 8 and versus change from baseline in IGA at Week 8 will be produced by treatment group as well as for both treatment combined. Spearman correlation coefficient will be presented. In addition, change from Baseline in DGLA versus change from baseline in IGA will also be plotted (along with Spearman correlation coefficient) at Week 8 as well as the change from baseline in DGLA at Week 8 versus the change from baseline in IGA at Week 10.

Descriptive statistics of level of DGLA will be presented by treatment, visit and responder status.

The analysis of the total fatty and interleukins data will not be covered in this SAP.

9 Reporting Conventions

P-values will be reported to 3 decimal places. If value is less than 0.001, then it will be shown as “<0.001”. The mean, SD, Median and inter-quantile will be reported to one decimal place greater than the original data. The minimum and maximum will use the same number of decimal places as the original data.

10 Technical Details

All statistical processing will be performed using SAS® software, Version 9.2, or higher.

11 Summary of Changes to the Protocol

Additional analyses (not included in the protocol) were added in the statistical analysis plan.

- Total and Free DGLA plasma level in relation with IGA results
- Respondeur analysis controlling for the information on IGA at Baseline
- Comparability of the discontinuation rates and of the reasons for discontinuation for both treatment groups

12 References

No applicable.

13 Mock Tables, Listings and Figures

All tables, listings and figures (TLF) will be generated through SAS.

The title will be unique for each TLF and self-explanatory. The header section will comprise of the Sponsor's name, the protocol number, the TLF number, the TLF title, the analysis population, and the page number (Page X of Y). The footer section of the table will include the date and time of the execution of the program, and the name of the program. All necessary footnotes will be provided to add clarity to the TLF.

The font will be "Courier New", 8-9 points, or similar. The orientation will be landscape with 1 inch margins. The tables and figures will be placed under Appendix 14 in the Clinical Study Report while the listings will be placed in the Appendix 16.

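### Fasting is required before the Day 0 and Week 4 blood draws but not the Week 8 draw, so Week 8 DGLA changes, and by inference triglyceride and glucose changes, compare samples of uncontrolled fasting state with a fasted baseline.

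*Protocol*

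**What the plan says.** Every fasting instruction in the protocol is attached to a dose.

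- The daily rule (5.3, repeated in 6.1): "Subjects will be required to start fasting at least 8 hours before drug administration upon waking".
- The clinic rule for the sampling visits (5.3): "Because dosing will occur at the clinic on Day 0 and week 4, subjects will be required to fast". That paragraph names Day 0, Week 4 and Week 8 as PK visits, then limits the fast to the first two.
- The visit lists for Baseline (7.2) and Week 4 (7.4): "Subjects are required to fast for at least 8 hours prior to study drug administration". The Week 8 list (7.5) has no such sentence.
- The flow chart footnote (Appendix A), on the row for on-site drug administration: "Subjects must be fasting for at least 8 hours before and 60 minutes after drug administration".

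PK blood at Day 0 and Week 4 must be taken before the dose (5.3, 8.2.4). For the third draw, 8.2.4 notes "no study drug administration at week 8 visit", and 6.1 puts the last dose on the preceding day. The only condition on the Week 8 PK draw in 7.5 concerns the drug, in the words also used at Week 4: "blood draw pharmacokinetics (if study medication was taken prior to the visit, subject must come back the next day".

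SAP section 6 takes as baseline the last value before the first dose. SAP section 8 then presents laboratory change from baseline and shift tables by time point, summarises DGLA by visit and responder status, and plots "change from Baseline in DGLA versus change from baseline in IGA" at Week 8 with a Spearman coefficient. Week 8 DGLA change is also plotted against IGA change at Week 10.

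**The concern.** A subject who follows the plan exactly fasts for the Day 0 and Week 4 draws. On the Week 8 morning there is no dose to take, so nothing stops that subject from having breakfast before the third draw. The Week 8 sample is then compared with a fasted baseline.

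The study drug is a fatty acid that also occurs in the diet (Protocol 1.2), and the sponsor standardises food around every dose. Leaving food open at one of three draws does not fit with that. The outputs exposed are within-arm DGLA change at Week 8, the correlations built on it, and Week 8 laboratory change and shifts for analytes that respond to a meal. Week 8 chemistry also decides whether safety laboratory tests are repeated at Week 10 (7.6, 8.2.3).

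The gap cannot be closed from the planned data. The diary in 6.3.3 asks about food only around a dose, and no dose is taken on the Week 8 morning.

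**Working it through.** **Step 1: the three draws side by side.**

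| Draw | Dose in clinic | Fast stated | Draw relative to dose |
|---|---|---|---|
| Day 0 | Yes | At least 8 h (5.3, 7.2) | Before |
| Week 4 | Yes | At least 8 h (5.3, 7.4) | Before |
| Week 8 | No | None (5.3, 7.5, 8.2.4, Appendix A) | Day after last dose |

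**Step 2: which analytes are covered.** For DGLA, the fasted state at Day 0 and Week 4 follows directly from the PK rule. For triglycerides and glucose it is an inference: 8.2.4 splits the chemistry draw to supply the interleukin aliquot, and it places the blood draws under its heading before dosing. The inference is weaker at Week 4, because the rule to return the next day names only PK draws. A Week 4 chemistry sample could therefore be post-dose if the subject had dosed at home.

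**Step 3: possible size.** The plan states no figure to reproduce, and the documents give neither a meal effect nor an SD for any of these analytes. What follows is illustration under assumed inputs.

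Let f be the share of subjects fed at Week 8. Let m be the shift caused by a meal, in units of the SD of change among fasted subjects. Feeding is taken as unrelated to the underlying change.

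- Shift in within-arm mean change = f × m
- Ratio of SDs of change = √(1 + f(1 − f)m²)

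Assumed ranges are f = 0.25 to 1.0 and m = 0.25 to 1.0.

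| f | m | Mean shift (SD) | SD ratio |
|---|---|---|---|
| 0.25 | 0.25 | 0.0625 | √(1 + 0.1875 × 0.0625) = 1.006 |
| 0.5 | 0.5 | 0.25 | √(1 + 0.25 × 0.25) = 1.031 |
| 0.5 | 1.0 | 0.50 | √(1 + 0.25 × 1) = 1.118 |
| 1.0 | 1.0 | 1.00 | √(1 + 0) = 1.000 |

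Over the whole range the mean shift runs from 0.06 to 1.0 SD and the rise in SD from 0% to 12%. The two do not peak together. The SD rises most when half the subjects are fed. If all are fed and shift by the same amount, the mean moves but ranks do not, so a Spearman coefficient is unchanged.

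**Step 4: between arms.** The expected difference moves by f × m in the DS107G arm minus f × m in the placebo arm. That is 0 when both arms share the same f and m.

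**The case against.** The strongest reply is that little depends on this. DGLA concentration is an exploratory endpoint (Protocol 3.3), and safety variables get no inferential statistics (SAP section 8). The tables show the two arms side by side, so a shift common to both would be visible. The correlations that use baseline DGLA are unaffected. Diet may also contribute little DGLA: Protocol 1.2 gives at most 0.115 g per measure, which is 0.115 / 2 = 5.75% of the 2 g daily dose. All of this stands and limits the weight of the point, although the dietary figure does not settle the acute effect of a meal on free DGLA.

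A second reply is that the laboratory panel was never meant to be fasting. Table 1 in 8.2.3 lists "Cholesterol (non-fasting), CK, Creatinine (Enzymatic), GGT, Glucose Random". A reader might see those labels as contradicting the fasted Day 0 and Week 4 visits. They do not: one panel serves screening and all later laboratory visits, fasting is required at only two of them, and a sample that happens to be fasted does not breach a label saying that fasting is not needed. What remains is that Week 8 change for these analytes still compares different sampling conditions.

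Third, the protocol is silent about food at Week 8. It does not tell subjects to eat, and it leaves detailed collection instructions to a central laboratory manual that is not among these documents. A reader might infer that Week 8 samples are fed, or partly fed. The text supports only that their fasting state is uncontrolled.

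**Conclusion.** The point holds as a minor one. Under the written plan, Week 8 DGLA has no fasting condition while its baseline and Week 4 values do. By inference the same applies to triglycerides and glucose. Within-arm change at Week 8 can shift, and the Week 8 DGLA–IGA correlations and laboratory shift tables can gain noise.

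The size is unknown. The range of 0.06 to 1.0 SD in mean change and 0% to 12% in the SD of change rests wholly on the assumed 25% to 100% fed and a meal effect of 0.25 to 1 SD.

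Three stronger readings are not supported:

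- **A biased treatment comparison.** This would need eating, or the effect of a meal, to differ between arms. Nothing in the documents suggests that, and both arms follow the same instructions. The primary IGA endpoint does not use these samples.
- **A large meal effect with marked attenuation of the correlations.** No document gives a meal effect, and the SAP's statistic is a rank correlation, to which the usual linear attenuation formula applies only approximately.
- **Rescue by reanalysing fasted samples.** Fasting state at Week 8 is not planned to be collected. The diary covers food around doses, and the SAP's compliance-log listing (16.2.5.3) holds missed doses and comments.

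**What to change.** Apply the fasting condition already used for the Day 0 and Week 4 draws to the scheduled Week 8 draw. State it in Protocol 5.3, in 7.5 and in the flow chart footnote, tied to the blood draw and not to the dose. Record time of last food at each of the three draws. The Week 8 visit doubles as the early termination visit, which is arranged as soon as possible (5.4), so at unscheduled early termination visits only record the time of last food.

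The cost is one more fasted morning for subjects who already fast before every dose, plus a short protocol change, a line in the visit reminder and one data field.

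If Week 8 visits have already taken place without food being recorded, label the Week 8 changes in DGLA, triglycerides and glucose as of unknown fasting state. Interpret them as differences between arms only, and give the Week 8 DGLA–IGA correlations the same label.

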5.4 Discontinuations

Subjects have the right to withdraw from the study at any time for any reason without penalty. The investigator also has the right to withdraw subjects from the study if he feels it is in the best interest of the subject or if the subject is uncooperative or non-compliant. It is understood by all concerned that an excessive rate of withdrawal can render the study un-interpretable; therefore, unnecessary withdrawal of subjects should be avoided. Should a subject decide to withdraw, all efforts will be made to complete and report the observations, particularly the follow-up examination, as thoroughly as possible.

The investigator or one of his or her staff members should contact the subject either by telephone or through a personal visit to determine as completely as possible the reason for the withdrawal, and record the reason in subject's source document and CRF. A complete final early termination (week 8) evaluation at the time of the subject's withdrawal should be made with an explanation of why the subject is withdrawing from the study. If the reason for removal of a subject is an adverse event or an abnormal laboratory test result, the principal specific event or test will be recorded. Subjects who discontinue the study before week 8 visit will be asked to come for an early termination visit as soon as possible and have the assessments listed at week 8 performed. They will also be asked to return two weeks later for the safety assessments listed at

week 10.

Reasons for discontinuation include:

- The investigator decides that the subject should be withdrawn. If this decision is made because of a serious or persistent adverse event, laboratory abnormality, or intercurrent illness, the study drug is to be discontinued and appropriate measures are to be taken. The investigator will notify the Sponsor or designee immediately.
- The subject or attending physician requests that the subject be withdrawn from the study.
- The subject for any reason requires treatment with another therapeutic agent that has been demonstrated to be effective for treatment of the study indication. In this case, discontinuation from the study occurs immediately upon introduction of the new agent.
- The subject is lost to follow-up, in this case, a reasonable attempt to contact the subject and ascertain his/her status must be made and these attempts must be documented.
- Serious protocol violation, including persistent non-compliance.
- The Sponsor or Regulatory Authorities, for any reason, stops the study. All subjects will be discontinued from the study and notified of the reasons for the discontinuation.
- Pregnancy at any time during the study.
- Other: the subject may withdraw from the study for any other reason, including withdrawal of consent.

6 TREATMENT

[figure not shown]
6.1 Treatment Administration

Subjects who fulfill all the inclusion and none of the exclusion criteria may be accepted in the study. Each subject must read and sign an informed consent form prior to any screening procedures being performed. This study involves a comparison of DS107G (2 g) with placebo, administered orally once daily upon waking for a total duration of 8 weeks. The last study drug administration should occur on the day preceding week 8 visit / Early Termination (ET) visit. Subjects will be randomized to one of the two treatment groups in a 1:1 ratio:

- Treatment group A: 2 grams DS107G (4 capsules)
- Treatment group B: 2 grams placebo capsules (4 capsules)

Subjects will be required to start fasting at least 8 hours before drug administration upon waking. Fasting will continue for at least 60 minutes following drug administration, after which subjects can have breakfast. Water will be allowed at all times during the fasting period, but no other fluids will be permitted. Medication(s) for other conditions that are permitted in the study can be taken as usual.

Blister packs will consist of 7 rows of 4 capsules. Each row constitutes one daily dose. Subjects will be instructed to take the 4 capsules **from left to right**, top to bottom, as shown below:

6.2 Study Treatment

6.2.1 ***Description***

DS107G capsules will be provided by Dignity Sciences as opaque, oval soft gelatin capsules containing 500mg of DGLA free fatty acid (FFA).

Placebo capsules will be also provided by Dignity Sciences as opaque, oval soft gelatin capsules containing 500mg of liquid paraffin.

DS107G capsules will be supplied in manufactured form (blinded), packaged in aluminum foil blisters of 28 units. Placebo will be presented in identical blisters and packs and stored/packaged the same as DS107G capsules. Study medication will be labelled according to US and Canadian regulations.

6.2.2 ***Storage Conditions***

The study medication will be provided by the sponsor to the investigator and will be kept, on site, in a locked room or cabinet with limited access. DS107G and placebo capsules should be stored at a controlled room temperature between 15-30°C and will only be supplied to subjects in the trial under the supervision of the investigator.

6.2.3 ***Study Drug Dispensing and Return***

Study drug will be dispensed by the study site to the subject at each study visit. Subjects are to return all study drug blister packs (used and unused) to the study site. The capsules within blister packs will be counted prior to dispensing and upon return and the counts will be recorded in the source documents and eCRF. Each subject is to be instructed on the importance of returning study drug at the next study visit. If a subject does not return study drug, he/she will be instructed to return it as soon as possible.

6.2.4 ***Drug Accountability***

The investigator is responsible for maintaining accurate records of the study medication received initially, the study drug dispensed/used, the returned medication by subjects and the medication destroyed or returned to the Sponsor or designee. All study drug accountability forms and treatment logs must be retained in the Investigator's study file. These records must be available for inspection by the Sponsor, its designees or by regulatory agencies at any time.

Used drug boxes/blister packs will be stored safely until destruction and must be accounted for by the investigator. The study monitor will perform drug accountability for all study drug at the site and assist in returning study drug, including used and unused study drug to the Sponsor or designee. After verification of the drug accountability by the sponsor, the investigator will ensure proper destruction or return of the remaining study product.

Any study medication accidentally or deliberately destroyed will be accounted for. Any discrepancies between amounts dispensed and returned will be explained.

Drug inventory and accountability records will be maintained at each site as per GCP/ICH guidelines.

6.2.5 *Method of Assignment to Treatment*

Approximately 100 patients will be randomized into double-blind treatment groups in a 1:1 ratio by an Interactive Web Response System (IWRS) or Interactive Voice Response System (IVRS), as follows:

- Treatment group A: 2 grams DS107G (4 capsules)
- Treatment group B: 2 grams placebo capsules (4 capsules)

A randomization list permuted blocks and stratified by site will be generated by Dignity Sciences or its designee. The randomization schedule with study drug assignments will be generated prior to the start of the study and will be known only to the individuals responsible for labeling the study drug. The IVRS or IWRS will assign a study drug kit number to each subject and the contents will be based on the randomization code.

At the investigational site, each subject will be assigned a patient identifier number during screening that will be used on all patient documentation. The patient identifier number will contain the site number and the patient number assigned in numerical order at the screening visit (e.g.: 02-010 for the tenth patient screened at the site #02). Numbers will be assigned in ascending order starting with 001.

6.2.6 *Rationale for Selection and Timing of Doses in the Study*

Doses up to 4 g have been well tolerated in healthy subjects. The dose of 2 g has been selected as the tested dose in the current study based primarily on the pharmacokinetic results from the Phase I trial which suggested saturable skin levels of total DGLA with repeated oral dosing of greater than 2g per day.

In addition the following factors were considered:

- (a) there were less frequent transient gastrointestinal instances recorded at a dose of 2g compared to 4g daily
- (b) the number of capsules (4) administered daily. A higher dose would be possible but is deemed less desirable as too many capsules may have a negative impact on patient adherence to treatment.

6.2.7 *Breaking of Study Blinding*

At all times, treatment and randomization information will be kept confidential and will not be released to the investigator, the study staff, the CRO or the sponsor's study team until following the conclusion of the study.

Blinding codes should only be broken in emergency situations for reasons of subject safety. The method will be either a manual or electronic process. When the blind for a subject has been broken, the reason must be fully documented. Whenever possible, the investigator should contact the Sponsor or its designee before breaking the blind. If the blind is broken, the investigator should promptly inform the Medical Monitor. Documentation of breaking the blind should be recorded with the date and time the blind was broken, and the names of the personnel involved.

The subject for whom the blind has been broken will be discontinued from the study and undergo the early termination (ET) procedures listed at the Week 8 visit. They will be also asked to return two weeks after the early termination visit for the safety assessments listed at Week 10. In cases where there are ethical reasons to have the subject remain in the study, the investigator must obtain specific approval from the Sponsor or its designee for the subject to continue in the study.

